III. Method Comparison Study Protocol

Protocol based on the following guidance documents:

Clinical & Laboratory Standards Institute (CLSI). *Method Comparison and Bias Estimation Using Patient Samples; Approved Guideline – Second Edition. EP9-A2.*

Purpose

This protocol is designed to investigate how Allegro results compare to a recognized central laboratory reference method. These studies are important in order to establish the relationship between the Allegro System and the reference method with respect to statistical correlation and measurement bias. This protocol is designed and recommended for the Allegro System.

Background

Good practice dictates that the performance of medical devices such as the Allegro System be verified before the conductance of clinical studies. Verification studies include: method comparisons to determine how the results of the Allegro Systems compare to a recognized reference method, studies of imprecision to determine the reproducibility of the various tests available on the Allegro to determine the analytical trueness of the Allegro measurements. The protocol below describes how to conduct a method comparison (Allegro vs. Reference Analyser).

Materials Needed

- Nova Biomedical Allegro
- Allegro Glycaemic Control Cartridges
- Nova Biomedical Allegro Quality Control (QC) Solution
- Reference Analyzer and reagents
- 2mL plastic microcentrifuge tubes for decanting EDTA samples
- Plastic 2mL disposable pipettes
- Full range of adjustable pipettes and tips
- If required appropriate Spiking stock solutions

Important Factors to Consider

Tests: HbA1c

Sample Type:

- Capillary blood (from finger stick)
- Fresh venous whole blood with anticoagulants ethylenediamine tetra-acetic acid (EDTA); Li heparin; Na heparin

Sample Size: 1.5 µL

Time per HbA1c: 6.25 mins

Linear Range of Operation for HbA1c: 4-15% (20.2 - 140.4 mmol/L)

Potential Interferences

HbA1c measurement is not affected by Hb variants: HbAc, HbAD, HbAE, HbF, HbAG and HbAS

Control Levels:

The Allegro supports two levels of controls. The following are suggested ranges for each parameter and level:

HbA1c:

Low Level Target: ~5% (~31.1 mmol/mol)

High Level Target: ~10% (~85.5 mmol/mol)

Normal Values

HbA1c:- A normal non-diabetic HbA1c is <5.5% (36mmol/mol). In diabetes about **6.5%** (48 mmol/mol) is good.

Procedure

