1. Fill out the requested information (Allegro serial numbers, cartridge lot numbers, QC lot numbers, QC ranges) on the provided Data Sheets (see Appendix).
2. Perform quality control runs on the Allegro being evaluated and the reference analyzer. Record the results for all systems on the Data Sheet and make sure the results are within the manufacturer's control range. **Proceed with testing only if all control results are within range.**
3. Select 40-50 fresh discarded HbA1c EDTA samples that cover the measuring range if possible.
4. Ensure adequate mixing before analysis.
5. Cartridges are stored at 4° each cartridge the HbA1c cartridge can be used cold
6. Run all samples in duplicate on Allegro following analysis on the reference analyser. Cartridges Allegro, the HbA1c cartridge can only be run in the 600nm channel which is on the right hand side of the analyser.
7. Collect, Review and collate data.
8. **Total Analysis Time:** 6.25 mins x 80 - 100 = 500 - 625 mins. Approx. 8.3 – 10.4 hrs plus preparation time
9. To reduce analysis time consider running samples in singles or perhaps less samples in duplicate whichever best suits site

Data Analysis

As part of this study paired HbA1c measurements will be collected. Analysis of accuracy is based on pairing individual results from the Allegro with the corresponding reference analyser measurement and calculating the difference (bias). Scatter plots and linear regression analysis are appropriate tools to assess the relationship between the Allegro results and the reference analyzer. Moreover, Bland-Altman plots can be used to assess the bias relative to the range studied. Investigators are referred to organizations such as CLSI and the International Standards Organization (ISO) which offer published acceptance criteria [2]. The validity of the conclusions is dependent on experimental design, chiefly number of samples, the distribution of results, and the calibration of the reference analyzer.

Data Review

This data will be summarized in a summary report which will also include an assessment of precision. This report should be reviewed and signed off by the study site principal investigator. Results of this laboratory evaluation can be used to document verification of the Allegro System performance prior to the conductance of clinical studies.

References

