1. Clinical & Laboratory Standards Institute (CLSI). *Method Comparison and Bias Estimation Using Patient Samples; Approved Guideline – Second Edition. EP9-A2.*

Appendix 4

Method Comparison Data Collection Sheet (Case Report Form)

Study Site: _____ Date of Study: _____

System Operator(s): _____

Specimen Type (Venous EDTA Whole Blood) _____

Reference Analyzer _____

	System Name		
	System Serial #		
	Cartridge Lot #		
Low QC	Range:		
High QC	Range:		
Specimen ID	Reference Analyzer Result % or mmol/mol	HbA1c result % or mmol/mol	HbA1c result % or mmol/mol
1			
2			
3			
4			
5			
6			
7			
8			
9			
10			
11			
12			
13			
14			
15			
16			
17			
18			
19			
20			
21			
22			
23			
24			
25			
26			
27			
28			
29			
30			

Specimen ID	System Name		
	System Serial #		
	Cart Lot #		
	Reference Analyzer Result % or mmol/mol	HbA1c result % or mmol/mol	HbA1c result % or mmol/mol
31			
32			
33			
34			
35			
36			
37			
38			
39			
40			
41			
42			
43			
44			
45			
46			
47			
48			
48			
49			
50			
51			
52			
53			
54			
55			
56			
57			
58			
59			
60			
61			
62			
63			
64			
65			
66			
67			
68			
69			
70			
71			
72			
73			

	System Name		
	System Serial #		
	Cart Lot #		
Specimen ID	Reference Analyzer Result % or mmol/mol	HbA1c result % or mmol/mol	HbA1c result % or mmol/mol
74			
75			
76			
77			
78			
79			
80			
81			
82			
83			
84			
85			
86			
87			
88			
89			
90			
91			
92			
93			
94			
95			
96			
97			
98			
99			
100			

Name of Person Collecting Data: _____

Signature of Person Collecting Data: _____

Date: _____

2. HbA1c

Summary Report Template

HbA1c Summary Report

Date:

Report Author:

Study Site:

Study Site Principal Investigator/Department:

Materials and Methods

See Protocols I-IV. *Any deviations from protocol should be noted here.*

Summary of Results

I. Precision Studies

Table 1. **HbA1c Within-Day** Precision for Allegro

	Low HbA1c	Mid HbA1c	High HbA1c
Mean % or mol/mol			
Standard Deviation			
%CV			
N			
Matrix			

Table 2. **HbA1c Between-Day** Precision for Allegro

	Low HbA1c	Mid HbA1c	High HbA1c
Mean % or mol/mol			
Standard Deviation			
%CV			
N			
Matrix			

II. Method Comparison

Table 5. Summary of Linear Regression Analysis Results HbA1C for Allegro

HbA1c	
Slope	
y-intercept (% or mmol/mol)	
R ²	
N	
HbA1c Range % or mmol/mol	

Table 6. Summary of Bland-Altman Results

HbA1c	
Mean Bias (% or mmol/mol)	
95% Limits of Agreement	
Lower	
Upper	
HbA1c (% or mmol/mol)	

Summary Findings

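### The HbA1c report gives one mean bias over whatever specimens are obtained; adding the bias at 5.5% and 6.5%, with confidence intervals, would be a near-costless improvement

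*Protocol*

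**What the plan says.** The Purpose of the HbA1c Method Comparison Study Protocol (section 2.III) names measurement bias as one of the two things to be established. Step 3 of its Procedure reads: "Select 40-50 fresh discarded HbA1c EDTA samples that cover the measuring range if possible". The stated measuring range is 4-15%.

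Data Analysis in 2.III defines bias as the difference between paired Allegro and reference results. It names scatter plots and linear regression as suitable tools and adds that "Bland-Altman plots can be used to assess the bias relative to the range studied". It requires no number from that plot.

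The HbA1c Summary Report Template sets the printed output:

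- Table 5 lists slope, "y-intercept (% or mmol/mol", R², N and the HbA1c range.
- Table 6 lists "Mean Bias (% or mmol/mol", the lower and upper "95% Limits of Agreement", and an HbA1c row.

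Neither table has a row for bias at a particular level, a standard error or a confidence interval.

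The only HbA1c values the protocol offers for reading a result stand under Normal Values in 2.III: "A normal non-diabetic HbA1c is <5.5% (36mmol/mol" and "In diabetes about 6.5% (48 mmol/mol) is good".

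**The concern.** A mean bias averages the differences over whatever specimens a site obtains. If the difference between the methods changes with HbA1c level, that average is the bias at the specimen mean and moves with the specimen mix. Both reference values, 5.5% and 6.5%, lie near the bottom of 4-15%. If the range is well covered, the specimen mean lies well above them.

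The limits of agreement do not fill the gap. They describe the spread of single differences, not the uncertainty of the estimated bias. The template's outputs therefore leave a reader without a direct statement of how large the bias is at these values, or how well it is known. The principal investigator signs off this report, and it may be used to document verification before clinical studies.

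**Working it through.** The protocol gives no expected bias, slope or SD of differences, so there is no figure to reproduce.

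**From the protocol:** range 4-15%; 40-50 specimens; reference values 5.5% and 6.5%.

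**Assumed:** specimens spread evenly over 4-15% (mean 9.5%; SD 3.30 for n = 40), with means of 8% and 7.5% as alternatives; slopes of 1.05 and 1.10; residual SD s of 0.2-0.4% HbA1c.

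**Step 1: bias by level.** With Allegro = a + b × reference, the bias at level x is a + (b − 1)x, and the mean bias is a + (b − 1) × specimen mean. The mean bias is zero when a = −(b − 1) × specimen mean. The bias at x is then (b − 1)(x − specimen mean).

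| Slope | Specimen mean | Intercept giving mean bias 0 | Bias at 5.5% | Bias at 6.5% |
|---|---|---|---|---|
| 1.05 | 9.5% | −0.475 | 0.05 × (−4.0) = −0.20 | 0.05 × (−3.0) = −0.15 |
| 1.10 | 9.5% | −0.95 | 0.10 × (−4.0) = −0.40 | 0.10 × (−3.0) = −0.30 |
| 1.05 | 8% | −0.40 | 0.05 × (−2.5) = −0.125 | 0.05 × (−1.5) = −0.075 |
| 1.05 | 7.5% | −0.375 | 0.05 × (−2.0) = −0.10 | 0.05 × (−1.0) = −0.05 |

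Slopes of 0.95 and 0.90 give the same sizes with the opposite sign.

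**Step 2: the offsetting intercept is essential.** With slope 1.05 and intercept 0, the mean bias is 0.05 × 9.5 = +0.475. A purely proportional error does not cancel over positive values.

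**Step 3: what the existing tables show.** In the first row above, Table 5 would print slope 1.05 and intercept −0.475. From these, −0.475 + 0.05 × 5.5 = −0.20, so the point bias can be recovered.

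**Step 4: whether the interval can be recovered.** Under ordinary least squares with one pair per specimen, Tables 5 and 6 together determine it:

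- SD of differences = (upper − lower limit of agreement)/3.92
- specimen mean = (mean bias − intercept)/(b − 1)
- specimen variance = (SD of differences)² / [(b − 1)² + b²(1 − R²)/R²]
- residual variance = b² × specimen variance × (1 − R²)/R² × (n − 1)/(n − 2)

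Unrounded entries return the half-width exactly. Rounded entries may not. A slope printed as 1.05 can stand for 1.045 to 1.055. With an intercept rounding error of 0.005 either side of −0.475, the implied specimen mean runs from 0.47/0.055 = 8.5% to 0.48/0.045 = 10.7%. The calculation breaks down when R² is given to two decimals, because 1 − R² is then mostly rounding. It is also undefined when the slope is exactly 1.

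**Step 5: width of the intervals proposed.** For n = 40 and even spread, the half-width at x is t(38) × s × √[1/40 + (x − 9.5)²/Sxx], with Sxx = 39 × 3.30² ≈ 424 and t(38) = 2.024. At 6.5% the root is √(0.025 + 9/424) = 0.215. The mean-bias half-width is t(39) × s/√40, with t(39) = 2.023.

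| s (% HbA1c) | Half-width at 6.5% | Half-width of mean bias |
|---|---|---|
| 0.2 | 0.087 | 0.064 |
| 0.3 | 0.131 | 0.096 |
| 0.4 | 0.174 | 0.128 |

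The last column takes the SD of differences as s. When the slope is not 1, level-dependent bias adds to that SD. At slope 1.05 and s = 0.2 it is √(0.2² + (0.05 × 3.30)²) = 0.26, and the mean-bias half-width becomes 2.023 × 0.26/√40 = 0.08.

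**The case against.** The strongest reply is that nothing is hidden or misstated. Mean bias with limits of agreement is a correct Bland-Altman summary, and slope, intercept, R² and N are a correct regression summary. Every cancelling case above would show in Table 5, and the Data Analysis text offers a plot of bias across the range. The raw pairs are on the collection sheet, so the report author can compute any interval. Cancellation also needs an intercept that happens to match the specimen mean. Confidence intervals are often left to a statistical analysis plan, which may exist. The slopes, SDs and even spread are all assumed, and at a specimen mean of 7.5% the effect at 6.5% falls to −0.05.

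Most of this stands, and it limits the point to an improvement. Three stronger readings are tempting, and the document does not support them:

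- **A proportional error alone can average to zero.** It cannot over positive values (Step 2).
- **The interval at 6.5% cannot be obtained.** It can be back-solved under ordinary least squares, but only from nearly unrounded entries and a slope different from 1.
- **5.5% and 6.5% are decision limits that the report fails to test.** They appear under Normal Values as background. The protocol sets no HbA1c bias limit and refers investigators to published criteria.

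What the reply does not remove is that this protocol itself contains the report template. In that template the headline bias shifts with the specimen mix and no bias estimate carries an interval. An investigator signing the report should not have to reconstruct one from rounded entries. N is also ambiguous: individual results are paired, and sites may run singles, duplicates or fewer samples in duplicate, so N may count pairs that are not independent.

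**Conclusion.** The point holds as a low-cost improvement to the HbA1c report, not as an error in the plan. The template reports bias as one mean over the specimens obtained, plus a point slope and intercept. It gives no interval for any bias estimate and no bias at a named level.

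Under assumed slopes of 1.05 to 1.10 with an offsetting intercept and a specimen mean of 9.5%, a mean bias of 0 coexists with −0.20 to −0.40% HbA1c at 5.5% and −0.15 to −0.30 at 6.5%. The effect shrinks as the specimen mean approaches the reference values: at slope 1.05 and a mean of 8%, it is −0.08 at 6.5%. These figures show what is possible. The protocol gives no evidence that the analyser behaves this way, and Table 5 would expose the pattern if it did.

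**What to change.** In Data Analysis of 2.III and in Table 6 of the HbA1c report:

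1. Add the predicted Allegro-minus-reference bias, with a 95% confidence interval, at 5.5% (36 mmol/mol) and 6.5% (48 mmol/mol). Take it from the fitted relation, using one difference per specimen, with duplicates averaged first.
2. Add a 95% confidence interval to the mean bias.
3. Base the Summary Findings on bias on these results as well as on the mean.

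The cost is two or three more table entries from data already collected, with no extra specimens or runs. The intervals at these levels will be wider than the one for the mean: at 6.5%, about 0.09-0.17 against 0.06-0.13% HbA1c for 40 specimens, under the residual SD and even spread assumed above.

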Urine Albumin and Creatinine:

Low Level Target: **Urine Albumin ~50 mg/L** **Creatinine ~85 mg/dL (~8 mmol/L)**

High Level Target: **Urine Albumin ~180 mg/L** **Creatinine ~220 mg/dL (~20 mmol/L)**

Please note that urine creatinine and Albumin are processed at the same time and can be run in both channels.

Procedure

1. Fill out the requested information (Allegro serial numbers, cartridge lot numbers, QC lot numbers, QC ranges) on the provided Data Sheets (see Appendix).
2. Perform quality control runs on the Allegro being evaluated and the reference analyzer. Record the results for all systems on the Data Sheet and make sure the results are within the manufacturer's control range. **Proceed with testing only if all control results are within range.**
3. Select low, med and high levels of both urine creatinine and Albumin, ideally using discarded random urine collections or, if these are not available, then urine samples that have been spiked with appropriate concentrations of creatinine spiking solution and/or human Albumin (**may need to be tested for homogeneity**).
4. Suggested concentrations for low, medium and high samples: -

	Urine Creatinine	Urine Albumin
Low Target	~25-30 mg/dL (~2.2-2.7mmol/L)	~10-15 mg/L
Medium Target	~200 mg/dL (~18 mmol/L)	~40 mg/L
High Target	~ 400-450 mg/dL (~35-40 mmol/L)	~150-200 mg/L
5. Ensure adequate mixing before analysis.
6. Cartridges are stored at 4° each cartridge requires 10-15 mins warm up time so consider this requirement when planning study needs.
7. Run each Level 10 times on Allegro, consider running only in one channel to reduce variability. Record results on Data Collection Sheet.
8. Total Analysis Time: 7 mins x 10 = 70 mins per level. 210 mins for all levels. Approx. 3.5 hrs plus preparation time.

Data Analysis

The within-run precision of the Allegro be assessed by calculating the % coefficient of variation (%CV) from the mean and standard deviation from the replicate measurements. Acceptability criteria are determined by the medical director and/or institution. Investigators are referred to organizations such as CLSI and the International Standards Organization (ISO) which offer published acceptance criteria [1].

Data Review

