Name of Person Collecting Data: _____

Signature of Person Collecting Data: _____

Date: _____

I. Urine Creatinine and Urine Albumin

III. Method Comparison Study Protocol

Protocol based on the following guidance documents:

Clinical & Laboratory Standards Institute (CLSI). *Method Comparison and Bias Estimation Using Patient Samples; Approved Guideline – Second Edition. EP9-A2.*

Purpose

This protocol is designed to investigate how Allegro results compare to a recognized central laboratory reference method. These studies are important in order to establish the relationship between the Allegro System and the reference method with respect to statistical correlation and measurement bias. This protocol is designed and recommended for the Allegro System.

Background

Good practice dictates that the performance of medical devices such as the Allegro System be verified before the conductance of clinical studies. Verification studies include: method comparisons to determine how the results of the Allegro Systems compare to a recognized reference method, studies of imprecision to determine the reproducibility of the various tests available on the Allegro, and to determine the analytical trueness of the Allegro measurements. The protocol below describes how to conduct a method comparison (Allegro vs. Reference Method).

Materials Needed

- Nova Biomedical Allegro
- Allegro Kidney Function Cartridges
- Nova Biomedical Allegro Quality Control (QC) Solution
- Reference Analyzer and reagents
- 2mL plastic tubes for decanting urine samples
- Plastic 2mL disposable pipettes
- Full range of adjustable pipettes and tips
- If required appropriate Spiking stock solutions

Important Factors to Consider

Tests: Urine Creatinine and urine Albumin

Sample Type: Fresh random urine

Sample Size: 25 μ L

Time per UABCR: 7 mins

Linear Range of Operation: 15-500 mg/dL (13.0-44.2 mmol/L)

Linear Range of Operation for Urine Albumin: 3-300 mg/L

Expected Normal Values

Urine Creatinine: For a random urine sample, >12 Years Male 20-370 mg/dL (1.8- 32.7 mmol/L), >12 Years Female 20 – 320 mg/dL (1.8-28.3 mmol/L)

Urine Albumin: For a random urine sample, normal values are typically 0 to 30 mg/L

Control Levels:

The Allegro supports two levels of controls. The following are suggested ranges for each parameter and level:

Urine Albumin and Creatinine:

Low Level Target:	Urine Albumin ~50 mg/L	Creatinine ~85mg/dL (~8 mmol/L)

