High Level Target:	Urine Albumin ~180 mg/L	Creatinine ~220 mg/dL (~20 mmol/L)

Please note that urine creatinine and urine Albumin are processed at the same time and can be run in both channels

Procedure

1. Fill out the requested information (Allegro serial numbers, cartridge lot numbers, QC lot numbers, QC ranges) on the provided Data Sheets (see Appendix).
2. Perform quality control runs on the Allegro being evaluated and the reference analyzer. Record the results for all systems on the Data Sheet and make sure the results are within the manufacturer's control range. **Proceed with testing only if all control results are within range.**
3. 40-50 fresh (within 24hrs) discarded random urine samples should be collected and run in duplicate on Allegro. Again spiking with creatinine spiking solutions and human Albumin may be required to cover the measuring range.
4. Ensure adequate mixing before analysis.
5. Samples should be analysed promptly on the reference analyser.
7. Cartridges are stored at 4° each cartridge requires 10-15 mins warm up time so consider this requirement when planning study needs.
8. Analyse all samples in duplicate on the Allegro using the same channel to reduce variability
9. Collect, Review and collate data.
10. Total Analysis Time: 7 mins x 80-100 =560 -700 mins. Approx. 9.3 – 11.6 hrs plus preparation time
11. To reduce analysis time consider running samples in singles or perhaps less samples in duplicate whichever best suits site

Data Analysis

As part of this study paired urine creatinine and urine Albumin measurements will be collected. Analysis of accuracy is based on pairing individual results from the Allegro with the corresponding reference analyser measurement and calculating the difference (bias). Scatter plots and linear regression analysis are appropriate tools to assess the relationship between the Allegro results and the reference analyzer. Moreover Bland-Altman plots can be used to assess the bias relative to the range of urine creatinine and urine Albumin concentrations studied. Investigators are referred to organizations such as CLSI and the International Standards Organization (ISO) which offer published acceptance criteria [1, 2]. The validity of the conclusions is dependent on experimental design, chiefly number of samples, the distribution of results, and the calibration of the reference analyzer.

Data Review

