This data will be summarized in a summary report which will also include an assessment of precision. This report should be reviewed and signed off by the study site principal investigator. Results of this laboratory evaluation can be used to document verification of the Allegro System performance prior to the conductance of clinical studies.

References

1. Clinical & Laboratory Standards Institute (CLSI). *Method Comparison and Bias Estimation Using Patient Samples; Approved Guideline – Second Edition. EP9-A2.*

Appendix 4

Method Comparison Data Collection Sheet (Case Report Form)

Study Site: _____ Date of Study: _____

System Operator(s): _____

Specimen Type (Urine) _____

Reference Analyzer _____

	System Name					
	System Serial #					
	Cartridge Lot #					
Low QC	Range:					
High QC	Range:					
Specimen ID	Urine Creat Result mg/dL or mmol/L	Urine Creat Result mg/dL or mmol/L	Reference Analyzer Result Urine Creat mg/dL or mmol/L	Urine Albumin Result mg/L or g/L	Urine Albumin Result mg/L or g/L	Reference Analyser Result Urine Albumin mg/L or g/L
1						
2						
3						
4						
5						
6						
7						
8						
9						
10						
11						
12						
13						
14						
15						
16						
17						
18						
19						
20						
21						
22						
23						
24						
25						
26						

27						
28						
29						
30						

Method Comparison Data Collection Sheet (Case Report Form)

Specimen ID	System Name					
	System Serial #					
	Cart Lot #					
	Urine Creat Result mg/dL or mmol/L	Urine Creat Result mg/dL or mmol/L	Reference Analyzer Result Urine Creat mg/dL or mmol/L	Urine Albumin Result mg/L or g/L	Urine Albumin Result mg/L or g/L	Reference Analyser Result Urine Albumin mg/L or g/L
31						
32						
33						
34						
35						
36						
37						
38						
39						
40						
41						
42						
43						
44						
45						
46						
47						
48						
48						
49						
50						
51						
52						
53						
54						
55						
56						
57						
58						
59						
60						
61						
62						
63						
64						
65						

66						
67						
68						
69						
70						
71						
72						

Method Comparison Data Collection Sheet (Case Report Form)

Specimen ID	System Name					
	System Serial #					
	Cart Lot #					
	Urine Creat Result mg/dL or mmol/L	Urine Creat Result mg/dL or mmol/L	Reference Analyzer Result Urine Creat mg/dL or mmol/L	Urine Albumin Result mg/L or g/L	Urine Albumin Result mg/L or g/L	Reference Analyser Result Urine Albumin mg/L or g/L
73						
74						
75						
76						

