High Level Target:	~ 240 mg/dL (~6.21 mmol/L)	~300 mg/dL (~3.39 mmol/L)	~60 mg/dL (1.55 mmol/L) (~1.55 mmol/L)

Procedure

1. Fill out the requested information (Allegro serial numbers, cartridge lot numbers, QC lot numbers, QC ranges) on the provided Data Sheets (see Appendix).
2. Perform quality control runs on the Allegro being evaluated and the reference analyzer. Record the results for all systems on the Data Sheet and make sure the results are within the manufacturer's control range. **Proceed with testing only if all control results are within range.**
3. 40-50 freshly collected/discarded whole blood venous, Na or Lithium heparin samples should be selected, that if possible, cover the analytical range across all analytes. Again spiking with appropriate spiking solutions may be required to completely cover the analytical range.
4. Ensure adequate mixing before analysis.
5. Analyse all samples in duplicate on the Allegro.
6. Samples should be spun down promptly (plasma) and then be analysed on the reference analyser.
7. Cartridges are stored at 4° each cartridge **the lipids cartridge is only stable at RT for 1 hour**
8. Run all samples in duplicate Allegro, the Lipids cartridge can only be run in the 660nm channel which is on the left hand side of the analyser.
9. Collect, Review and collate data.
10. Total Analysis Time: 10 mins x 80-100 = 800-1000 mins. Approx. 13.3 – 16.6 hrs plus preparation time
11. To reduce analysis time consider running samples in singles or perhaps less samples in duplicate whichever best suits site

Data Analysis

As part of this study paired total cholesterol, triglycerides and HDL cholesterol measurements will be collected. Analysis of accuracy is based on pairing individual results from the Allegro with the corresponding reference analyser measurement and calculating the difference (bias). Scatter plots and linear regression analysis are appropriate tools to assess the relationship between the Allegro results and the reference analyzer. Moreover, Bland-Altman plots can be used to assess the bias relative to the range of urine creatinine and urine Albumin concentrations studied. Investigators are referred to organizations such as CLSI and the International Standards Organization (ISO) which offer published acceptance criteria [1, 2]. The validity of the conclusions is dependent on experimental design, chiefly number of samples, the distribution of results, and the calibration of the reference analyzer.

Data Review

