This data will be summarized in a summary report which will also include an assessment of precision. This report should be reviewed and signed off by the study site principal investigator. Results of this laboratory evaluation can be used to document verification of the Allegro System performance prior to the conductance of clinical studies.

References

1. Clinical & Laboratory Standards Institute (CLSI). *Method Comparison and Bias Estimation Using Patient Samples; Approved Guideline – Second Edition. EP9-A2.*

Appendix 4

Method Comparison Data Collection Sheet (Case Report Form)

Study Site: _____ Date of Study: _____

System Operator(s): _____

Specimen Type (Na or Lithium heparin venous blood) _____

Reference Analyzer Result mg/dL or mmol/L Total Cholesterol _____

Reference Analyzer Result mg/dL or mmol/L Triglycerides _____

Reference Analyzer Result mg/dL or mmol/L HDL Cholesterol _____

	System Name								
	System Serial #								
	Cartridge Lot #								
Low QC	Range:								
High QC	Range:								
Specimen ID	Total Chol mg/dL or mmol/L	Total Chol mg/dL or mmol/L	Reference Analyzer Result Total Chol (mg/dL or mmol/L)	Trigs mg/dL or mmol/L	Trigs mg/dL or mmol/L	Reference Analyzer Result Trig (mg/dL or mmol/L)	HDL Chol mg/dL or mmol/L	HDL Chol mg/dL or mmol/L	Reference Analyzer Result HDL Chol(mg/dL or mmol/L)
1									
2									
3									
4									
5									
6									
7									
8									
9									
10									
11									
12									
13									
14									
15									
16									
17									
18									
19									
20									
21									
22									
23									
24									
25									

26									
27									
28									
29									

Method Comparison Data Collection Sheet (Case Report Form)

Specimen ID	System Name								
	System Serial #								
	Cart Lot #								
	Total Chol mg/dL or mmol/L	Total Chol mg/dL or mmol/L	Reference Analyzer Result Total Chol (mg/dL or mmol/L)	Trigs mg/dL or mmol/L	Trigs mg/dL/ or mmol/L	Reference Analyzer Result Trig (mg/dL or mmol/L)	HDL Chol mg/dL or mmol/L	HDL Chol mg/dL or mmol/L	Reference Analyzer Result HDL Chol(mg/dL or mmol/L)
30									
31									
32									
33									
34									
35									
36									
37									
38									
39									
40									
41									
42									
43									
44									
45									
46									
47									
48									
48									
49									
50									
51									
52									
53									
54									
55									
56									
57									
58									
59									

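### Urine and lipid comparisons admit spiked specimens without a limit or a per-specimen marker, so a few spiked points could set the pooled slope and nobody could tell from the forms

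*Protocol*

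**What the plan says.** Both sections concerned allow spiking at Procedure step 3. For urine (1.III): "Again spiking with creatinine spiking solutions and human Albumin may be required to cover the measuring range". For lipids (3.III): "Again spiking with appropriate spiking solutions may be required to completely cover the analytical range". The lipid sample is described as "40-50 freshly collected/discarded whole blood venous, Na or Lithium heparin samples should be selected", and the urine study is also 40 to 50 specimens. Neither section limits how many may be spiked or asks that they be identified.

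The method comparison forms (Appendix 4 of each section) carry one specimen-type line in the form heading, "Specimen Type (Urine)" and "Specimen Type (Na or Lithium heparin venous blood)". Each row below holds a specimen ID and results, with nothing to show whether that specimen was spiked.

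The report templates give one slope, intercept, R², N and range per analyte (Tables 7 and 11) and one mean bias with limits of agreement (Tables 8 and 12). The precision tables have a row for the matrix; the comparison tables do not. Under Materials and Methods the template asks for deviations from protocol. Spiking is permitted, so it is not a deviation and nothing prompts its disclosure.

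The HbA1c comparison (2.III) differs. Its step 3 reads "Select 40-50 fresh discarded HbA1c EDTA samples that cover the measuring range if possible" and no step calls for spiking; spiking stock appears only in the materials list.

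**The concern.** Spiking raises concentration, so spiked specimens fill the upper part of the range. In least-squares regression, points far from the mean of x largely fix the slope. If few native samples are high, a handful of spiked specimens can determine the reported slope, and the report would not show it.

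This matters only if spiked and native material behave differently on the two methods. If they do, the pooled line can show a proportional error that patient samples do not have, or hide one that they do have. The results may be used to document performance before clinical studies, so a reader will take the slope as describing patient specimens. With no marker on the form, a later analysis plan that asked for a native-only result would have no field from which to build it.

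**Working it through.** The plan gives no figure on this point to reproduce. The following is an illustration.

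**Inputs from the Protocol.** N = 40, the lower end of 40 to 50. Upper limits of the linear range in 1.III and 3.III: albumin 300 mg/L; creatinine 500, triglyceride 600, total cholesterol 450 and HDL 100 mg/dL. Typical random urine: albumin 0 to 30 mg/L; creatinine 20 to 370 mg/dL (males over 12 years).

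**Assumptions, not in the Protocol.** Five of the 40 are spiked. The 35 native specimens are evenly spaced over albumin 5–30 mg/L, creatinine 20–370, triglyceride 50–200, total cholesterol 120–250 and HDL 25–70 mg/dL. The five spiked specimens are evenly spaced from above the native maximum up to the upper limit. Random error is left out, because it does not shift the expected slope.

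**Formulas.** Let x̄ be the mean of all 40, Sxx = Σ(x − x̄)² over all 40, and T = Σ(x − x̄)x over the spiked specimens only.

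- Share of the spread held by spiked points = Σ over spiked of (x − x̄)² / Sxx.
- Case A, native exact and spiked reading 10% low: pooled slope = 1 − 0.1·T/Sxx.
- Case B, native 10% low and spiked recovering fully: pooled slope = 0.9 + 0.1·T/Sxx.

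**Albumin in full.** The spiked values are 84, 138, 192, 246 and 300 (sum 960) and the native mean is 17.5. So x̄ = (35 × 17.5 + 960)/40 = 39.3.

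- Spiked sum of squares: 44.7² + 98.7² + 152.7² + 206.7² + 260.7² ≈ 145,727.
- Native sum of squares: about 1,930 around their own mean, plus 35 × 21.8² ≈ 16,653, giving 18,583.
- Sxx ≈ 164,310, so the share is 145,727/164,310 = 0.89.
- T ≈ 175,740 and T/Sxx = 1.070. Case A: 1 − 0.107 = 0.89. Case B: 0.9 + 0.107 = 1.01.

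**All analytes, same steps.**

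| Analyte | Spiked share of Sxx | T/Sxx | Case A slope (native truth 1.00) | Case B slope (native truth 0.90) |
|---|---|---|---|---|
| Albumin | 145,727/164,310 = 89% | 1.070 | 0.89 | 1.01 |
| Triglyceride | 443,846/567,595 = 78% | 1.181 | 0.88 | 1.02 |
| Total cholesterol | 147,018/217,926 = 67% | 1.448 | 0.86 | 1.04 |
| HDL | 6,639/13,790 = 48% | 1.157 | 0.88 | 1.02 |
| Creatinine | 251,794/665,108 = 38% | 0.756 | 0.92 | 0.98 |

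**Sensitivity.** With 2 to 10 spiked among 40 or 50, the same layout gives shares of 80–94% (albumin), 73–78% (triglyceride), 55–68% (total cholesterol), 31–53% (HDL) and 21–45% (creatinine).

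**Mean bias.** For albumin in case A the pooled mean bias is −0.1 × 960/40 = −2.4 mg/L although native bias is zero. In case B it is −0.1 × 35 × 17.5/40 = −1.5 mg/L, against a native-only −1.75 mg/L. So in case B the slope hides the native error while the mean bias still shows most of it.

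**The case against.** The strongest reply is that nothing in the documents says spiked material reads differently from native material; the 10% is an assumption. Spiking is also conditional, and if enough native high samples are found, few or none are needed. Native pathological samples in the upper range would reduce the leverage of any spiked points. The effect is weakest for creatinine and HDL. No pass/fail threshold in these sections is tied to the slope. All of this stands, and it limits the point to a risk that ought to be checkable.

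A reader might infer more, and the documents do not support it:

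- *That pooling contradicts the plan's own basis.* The phrase "Method Comparison and Bias Estimation Using Patient Samples" is the title of a cited guideline. The stated purpose is comparison with a central laboratory method, and the procedure openly permits spiking. What the guideline says about spiking cannot be checked here.
- *That the protocol itself doubts spiked specimens.* The remark that spiked urine "may need to be tested for homogeneity" belongs to within-day precision (1.I) and to urine only. Poor homogeneity would mainly add scatter; it does not imply a systematic difference.
- *That R² is inflated by spiking.* R² rises with any widening of the range, including by native high samples, and a marker would not cure that. The plan already warns that validity depends on the distribution of results, and its tables report the range.
- *That the information is lost for good.* Every row has a specimen ID, so preparation records kept by the site might identify the spiked specimens. The forms do not require such records, so this is a gap in traceability.
- *That native-only results must be the main ones.* That would leave the upper range, which spiking is there to cover, without a main estimate.

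A separate analysis plan could ask for a split analysis. It would still need the spiking status of each specimen, which these forms do not collect.

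**Conclusion.** The point holds for the urine and lipid comparisons as a defect of recording and reporting. Spiking is allowed without a limit, specimens are not marked, and results are pooled.

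Its size depends on assumed native ranges and on five spiked specimens of 40. Those five then carry about 38% (creatinine) to 89% (albumin) of the spread that fixes the slope. A 10% difference confined to spiked material would move a true native slope of 1.00 to about 0.86–0.92. A 10% native deficit with full recovery of spikes would appear as a slope of about 0.98–1.04 and be largely hidden. Whether any such difference exists is unknown, and the present forms would not reveal it. HbA1c, which has no spiking step, is outside the point. The change is worth making, but spiking itself is not at fault.

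**What to change.** - Add a native/spiked column to the 1.III and 3.III method comparison forms.
- State the number of spiked specimens for each analyte in Tables 7, 8, 11 and 12.
- Report slope, intercept, mean bias and limits of agreement both with and without the spiked specimens, and give the native range beside the native-only figures.

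Spiking stays available. The cost is one form column and a repeat of the analysis. The native-only result will cover a narrower range, and the report should say so. The column should be in place before specimens are collected, because afterwards the split would depend on whatever preparation records the site happened to keep.
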